**Aim 2b: To compare monocyte polarization and inflammatory gene expression at 6-weeks**

**Analysis Plan:** Comparison of expression of these markers between groups will be done with ANOVA. Alterations in the percent change in monocyte subsets will be correlated with both the primary end-point ( $\Delta$  PAV) and secondary end-points including change in HOMA-IR, SBP (central aortic) and PWV.

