### Secondary Efficacy Endpoints

Change in central aortic SBP, Change in central aortic DBP, Change in central aortic Mean BP, 24-hour mean ambulatory BP, 24-hour ambulatory diastolic blood pressure, and HOMA-IR.

Evaluate miRs involved in regulating MR expression and differentially regulated miRs as predictors of disease progression and response.

Compare monocyte inflammatory activation in Spironolactone vs placebo at 6-weeks.

Investigate pre-miR/mimics and antagonomirs to regulate NR3C2 expression and alternate macrophage phenotype in human macrophages.

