## **STUDY TREATMENTS**

### **Method of Assigning Subjects to Treatment Groups**

After the placebo run-in phase, eligibility with regards to blood pressure will be reassessed.

Up to 130 eligible patients will be randomly assigned to Spironolactone or placebo treatment groups in a 1:1 ratio using a computer-generated randomization scheme developed by the statistician.

All study participants will undergo a two week run-in period with placebo. Then study medication will be commenced at 12.5 mg Spironolactone or placebo and escalated to 25 mg Spironolactone or placebo over 4 weeks. Then the treatment phase will commence with tolerated dose of Spironolactone or placebo for 48 weeks.

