### Main Study Phase

TABLE 4	SCREEN		RUN-IN PHASE		RANDOMIZATION PHASE										
					DOSE ESCALATE				TREATMENT PHASE						
	MONTH*	M1	M1	M2	M2	M 2	M 3	M 5	M 7	M 9	M 11	M 12	M 13		
WEEK	W 1	W2	W3	W4	W5	W6	W8	W9	W11	W17	W25	W33	W41	W45	W53
VISIT NUMBER	0		1	2	3	4	5	6	TF1	7	TF2	TF3	TF4	8	
Screening Labs (BMP, Lipid panel, HbA1C, Urine sample Alb/Creat)	X														
Safety Lab (BMP)				X	X	X	Opti onal	X		X					X
History/ Targeted assessment		X								X					X
EKG		X													
Vital Signs or 24-hour BP cuff *( includes central aortic BP)	X	X	X*		X		X*		X						X
Phone Call								X		X	X	X			
MRI				X											X
Research Labs/Monocyte Studies, including PIP, PIIINP, CITP and chemokines CCL2, CX3, CL1, and CCL5				X			X								X
Insulin/Glucose (HOMA-IR)				X											X
HbA1C				X						X					X
Plasma Renin/Aldosterone				X											X
Medication Log		X			X		X	X	X	X	X	X	X		X
Pill counts			X				X		X						X
Dietary survey/instructions		X													X
Urine sample (Albumin/Creat)	X	X	X				X		X						X
Urine Na/K/Creat			X												
Interim Event log			X		X		X	X	X	X	X	X	X		X
Questionnaire & Instructions		X													

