## STATISTICAL METHODS AND CONSIDERATIONS

Prior to the analysis of the final study data, a detailed Statistical Analysis Plan (SAP) will be written describing all analyses that will be performed. The SAP will contain any modifications to the analysis plan described below. General Statistical Considerations: All the tests are two-sided. We use log transformations for most continuous measures, and arc-sin square root transformations for percentages, both of which have excellent variance stabilizing properties for pooling variance.

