**Analysis Plan:** After distributions are checked and outliers are investigated for veracity, descriptive statistics by treatment arm will be reported for patient demographics and important potential confounding variables at baseline. These will include age, gender, BMI, baseline blood pressure, HbA1c, 24-hour urine Na, plasma and renin/aldo activity at baseline, HOMA-IR, HDL and non-HDL cholesterol. To analyze these data (primary end points and secondary outcome measures), linear mixed models with group (drug/placebo), baseline plaque volume, time points (before/after), stratification variables (age, high-risk feature) and other potential confounders (such as demographics and other comorbidities) as well as a patient random effects (to account for the correlation of measures within same patient) will be used. Different covariance structures will be used and best model will be selected based on AIC criteria by first fitting most complicated mean structure model, selecting the best covariance structure, then selecting the best mean structure, using SAS procedure GLIMMIX or MIXED) and convergence and model performance will be evaluated using SAS fit statistics (e.g. AIC criteria). Clinically relevant interactions will also be included in the models. Forward stepwise selection followed by backward elimination will be used to retain features with the greatest combined prediction power while maintaining parsimony using a training data set. Traditional methods, such as AIC and BIC involve a combinatorial optimization problem, which is NP-hard, with computational time increasing exponentially with the dimensionality. The expensive computational cost makes traditional procedures infeasible for high-dimensional data analysis. To overcome this, penalized likelihood maximization and penalized risk minimization have been intensively used for classification. Penalized methods with  $L_p$ -penalty, especially when  $p \leq 1$ , automatically perform variable selection by removing predictors with very small estimated coefficients. Fan et al. proposed SCAD-penalty with better oracle properties 131 . It automatically selects features and avoids excessive estimation bias compared to  $L_1$ -penalty. We will use penalized methods for classification in order to avoid over-fitting problems by producing sparse solutions via feature selection.

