**Aim 2c: To evaluate miRs expression to predict atherosclerosis and response**

In an exploratory analysis, similar model selection strategy as in aim 1 will be applied which will include traditional risk factors. Based on the model we generated in aim 1, we will add miRNAs as additional factors (singly and in combination). Using this model, we will be able to test the effect of miRNA(s) at baseline on the rate of atherosclerosis progression and to identify patients who demonstrate greater response (e.g. decreases in PAV). The first half of patients (n=30 per group) will be used to build our model (training stage). The rest of the patients enrolled will be used to validate this model (validation stage). Features that are dropped from the model because of redundancies will be retained for further univariate testing in the validation data. Combining biological and clinical deliberations with statistical

results will likely generate a few alternative models with similar prediction accuracy. Cross-validation will be used to evaluate a classifier's prediction accuracy and for choosing the best tuning parameters. The classifier's prediction accuracy will be the main objective of this aim. For sample size calculations, we use the method described by Dobbin et al. 183, 184, which is based on the assumption that the expected accuracy of the classifier is controlled within a percentage (tolerance) of the best possible classifier. Assuming a maximum tolerance of 5% (and at most a 2-fold difference in the differentially expressed miRNAs (assuming a median SD of 0.71), a sample size of n=60 total (training and validation sets) is required. Tolerance represents the difference in the probability of correct classification in the training sample with respect to the same probability from an optimal signature. This sample size does not guarantee that there will be differentially expressed miRNAs. Instead, this sample size will be enough to validate a differentially expressed miRNAs, if such miRNAs is found in the data. Baseline miRNAs will also be correlated with markers of alternate activation (CD206+ and CD163+ monocytes) and MR gene/protein expression.

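### Aim 2b names an ANOVA without a baseline term for the 6-week monocyte markers; adjusting for each marker's own baseline is an optional, nearly free gain in precision

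*Combined protocol and SAP*

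**What the plan says.** The monocyte comparison is listed under Secondary Efficacy Endpoints: "Compare monocyte inflammatory activation in Spironolactone vs placebo at 6-weeks". Its analysis is in the Aim 2b plan: "Comparison of expression of these markers between groups will be done with ANOVA". No covariate is named and the compared variable is not defined. The next sentence of that plan brings in change, but only for correlations: "Alterations in the percent change in monocyte subsets will be correlated with both the primary end-point".

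The scale is settled in the general statistical considerations: "We use log transformations for most continuous measures, and arc-sin square root transformations for percentages".

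Table 4 (Main Study Phase) has a row for "Research Labs/Monocyte Studies, including PIP, PIIINP, CITP and chemokines" with three marks. The table layout is broken in the text available, but the first mark appears to share a column with the first MRI.

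Two other places bear on the model. The Aim 1 analysis plan reads "To analyze these data (primary end points and secondary outcome measures), linear mixed models with group (drug/placebo), baseline plaque volume, time points (before/after", followed by stratification variables (age, high-risk feature), other confounders and patient random effects. The Aim 2c plan says "similar model selection strategy as in aim 1 will be applied which will include traditional risk factors". Aim 2b contains no such cross-reference.

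**The concern.** If the 6-week value is what the ANOVA compares, a pre-treatment measurement of the same marker goes unused in the treatment comparison. That baseline could remove part of the between-patient variance without any new data.

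If change is compared instead, the baseline is used inefficiently. For any correlation below 0.5 a change score is less precise than the 6-week value alone. The two readings therefore differ in power, and the plan does not choose between them. The 6-week value is the more natural reading, because both the endpoint and the aim heading refer to 6 weeks and change appears only in the correlation sentence.

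What is at stake is precision on a secondary, mechanistic endpoint that has no power target of its own.

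**Working it through.** **Trial size.** Aim 2b states no sample size, so the only anchor is the PAV calculation under Aim 1: 80% power, 1.5-fold difference, CV 0.83, alpha 0.05, two-sided. On the log scale SD = sqrt(ln(1 + 0.83²)) = 0.724 and the difference is ln 1.5 = 0.405. A t-based two-sample calculation gives 52 per group, and 104/0.80 = 130, so the plan's figures reproduce. As 52 is the completer number at 54 weeks, the number per arm at 6 weeks should lie between 52 and 65.

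**Assumed, because the documents are silent.** The baseline to 6-week correlation r; the starting power of the 6-week-value ANOVA (60, 80 or 90%); equal SD at both times.

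**Variance of the treatment effect relative to the 6-week-value ANOVA, n per arm.**
- ANCOVA, one baseline covariate: (1 − r²)(1 + 1/(2n − 4)). The second factor is 1 + 1/100 = 1.010 at n = 52 and 1 + 1/126 = 1.008 at n = 65.
- Change score: 2(1 − r).

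**Break-even.** Setting the ANCOVA ratio to 1 gives r = sqrt(1/(2n − 3)): sqrt(1/101) = 0.10 at n = 52 and sqrt(1/127) = 0.09 at n = 65. Against the change score, ANCOVA is more precise while (1 + r) × 1.010 < 2, that is, r below about 0.98.

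**Power** (noncentral t; 2n − 3 df for ANCOVA, 2n − 2 otherwise). At 52 per arm, for an effect of 0.438 SD, which has 60% power by 6-week-value ANOVA:

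| r | ANCOVA | Change score |
|---|---|---|
| 0 | 59.6% | 34.7% |
| 0.1 | 60.0% | 37.8% |
| 0.3 | 63.6% | 46.4% |
| 0.5 | 72.0% | 60.0% |
| 0.7 | 86.9% | 81.5% |

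Simulation agrees to within 0.3 point. At 65 per arm the same effect has 69.8% by 6-week-value ANOVA and 69.5, 69.9, 73.5, 81.4 and 93.3% by ANCOVA at the same values of r.

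**Sensitivity to the starting power, 52 per arm.** At r = 0.5 the ANCOVA gain is 12.0 points from 60%, 9.6 from 80% and 6.1 from 90%. At r = 0.2 it is about 1 point from any of these. At r = 0 the loss is about 0.4 point or less.

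**Missing baselines, 52 per arm.** If ANCOVA drops a fraction m of patients, n becomes 52(1 − m) and the ratio is divided by 1 − m.
- m = 5%: n = 49.4, slope factor 1 + 1/94.8 = 1.0105, break-even r = sqrt(1 − 0.95/1.0105) = about 0.25.
- m = 10%: n = 46.8, slope factor 1 + 1/89.6 = 1.0112, break-even r = sqrt(1 − 0.90/1.0112) = about 0.33.

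For the effect with 60% power, the losses at r = 0 are 2.7 and 5.0 points. Filling missing baselines with the pooled mean keeps all patients and the 1.010 factor. Adding a missing indicator makes two covariates: 1 + 2/(2n − 5) = 1 + 2/99 = 1.020. The loss at r = 0 is then about 0.9 point, and at m = 5% break-even is about sqrt((1 − 1/1.020)/0.95) = 0.14.

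**The case against.** The strongest counter-argument is that the Aim 1 plan already covers this endpoint. It assigns secondary outcome measures to mixed models with before and after time points, and the monocyte comparison is a listed secondary endpoint. On that reading the pre-treatment marker value already enters the model. This stands as an ambiguity. It does not settle the matter: the text sits under Aim 1, the only baseline covariate it names is plaque volume, and Aim 2b names a different method of its own. That Aim 2c borrows from Aim 1 while Aim 2b does not is weaker evidence, because what Aim 2c borrows is a strategy for selecting predictors.

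Second, the compared variable is unstated, so a reader should not infer that the plan definitely ignores the baseline. If change is analysed, the baseline is used, and the break-even of 0.10 does not apply; the comparison is then with the change score, which ANCOVA beats for r below about 0.98.

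Third, the columns of Table 4 cannot be relied on for timing. A baseline is still implied, at least for monocyte subsets, because percent change cannot be computed without one.

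Fourth, no power target is missed, and the protocol defers detail to a SAP still to be written. That limits the point to an optional improvement.

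**Conclusion.** The point holds as an optional gain in precision. It would be tempting to infer that the ANOVA is biased or invalid; randomisation makes it valid whichever variable is compared. It would also be tempting to quote a fixed loss of power, such as 12 points. The documents give no correlation, marker SD or effect size, so the gain is unknown. It is near nothing for r of 0.1 to 0.2 and material from about 0.3 to 0.5 upward, and it may differ between markers.

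What is firm is the asymmetry. With complete baselines the cost is about 1% of variance, 0.4 power point or less at r = 0, and break-even against the 6-week value is at r of about 0.10 or 0.09. That rests on equal SDs at the two times and 52 to 65 patients per arm. The low break-even is lost if patients without a baseline are dropped.

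**What to change.** In the SAP, name one model for Aim 2b and say that it governs this endpoint in place of the Aim 1 mixed model: an ANCOVA of the 6-week marker on treatment and the same marker's baseline, both on the scale already laid down (log, or arcsine square root for percentages).

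State a rule that keeps patients with no usable baseline, for example the baseline mean pooled across arms, with a missing indicator if wanted.

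Add age and the high-risk feature only if randomisation was stratified on them. The Aim 1 plan calls them stratification variables, but the section on assigning subjects mentions only allocation "using a computer-generated randomization scheme developed by the statistician". If unrelated to outcome, these two would cost a further 0.7 to 0.9 power point at 52 per arm (variance factor 1 + 3/98 = 1.031 in all, for r from 0 to 0.7 and the effect with 60% starting power).

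The cost is a few sentences in the SAP and no new data. The downside is the small loss if r is near 0, and the need to settle the missing-baseline rule in advance.

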## SUMMARY

Atherosclerosis is the leading cause of morbidity and mortality in Type II diabetes. A cell type called the monocyte/macrophage is critical to development and complications of atherosclerosis. This project will evaluate the effectiveness of a medication called Spironolactone in preventing atherosclerosis in Type II diabetes through its effects on cells such as the monocyte. Spironolactone has been demonstrated to be effective for the treatment of patients after a heart attack and stroke. We will evaluate the impact of Spironolactone in reducing atherosclerosis plaque and additionally evaluate its potential in changing inflammation. We envision that our strategy of simultaneously probing effect of a drug combined with analysis of mechanisms of action and predictive response will likely provide key information with which to design hard event (heart attack, stroke etc.) based trials.

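### Aim 2b correlates monocyte change with change in PAV, HOMA-IR, central SBP and PWV but specifies no adjustment for treatment arm, so a plain correlation would mix the drug's effect on both with the within-arm association

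*Combined protocol and SAP*

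**What the plan says.** Aim 2b has two analyses. The first compares arms: "Comparison of expression of these markers between groups will be done with ANOVA". The second relates monocyte change to outcome change: "Alterations in the percent change in monocyte subsets will be correlated with both the primary end-point" (change in PAV) and "secondary end-points including change in HOMA-IR, SBP (central aortic) and PWV". For this second analysis the plan names no arm term, no within-arm analysis and no partial correlation.

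A treatment term appears in the Aim 1 analysis plan, which specifies "linear mixed models with group (drug/placebo), baseline plaque volume, time points (before/after" and further covariates. The scope of that model is given as "To analyze these data (primary end points and secondary outcome measures". The Aim 2b correlation is not tied to it.

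The Summary sets out the premise that spironolactone acts by "preventing atherosclerosis in Type II diabetes through its effects on cells such as the monocyte". It also describes "our strategy of simultaneously probing effect of a drug combined with analysis of mechanisms of action and predictive response" as the project's strategy. Statistical Methods and Considerations promises a more detailed SAP before the final analysis. The text supplied says nothing more about this correlation.

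**The concern.** Both variables are measured after randomisation, and the trial hypothesises that the drug moves both. If it does, the two arms form two clouds of points displaced from each other. A single correlation through both clouds picks up that displacement even if, within each arm, a patient's plaque change has nothing to do with that patient's monocyte change.

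The error can also run the other way. A real within-arm association is diluted when the between-arm displacement runs against its sign.

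Aim 2b is the only analysis in the plan that relates monocyte change to plaque change. The effect of the drug on each variable separately is already tested by the ANOVA and the Aim 1 model. What the correlation can add is information within arms, and that is the part a pooled version contaminates.

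**Working it through.** **1. Reproduce the plan's PAV design effect.** Inputs from Aim 1 and Table 7: CV 0.83, 1.5-fold difference, 80% power, alpha 0.05. The tests are two-sided ("All the tests are two-sided").
- Log-scale SD = sqrt(ln(1 + 0.83²)) = 0.724.
- Difference = ln(1.5) = 0.405, so the standardised effect is 0.405/0.724 = 0.56 SD.
- The noncentral t calculation gives 52 per group, as stated, and matches all nine cells of Table 7. The normal approximation gives 51.
- 2 × 52 = 104 completers, and 104/0.80 = 130 recruited, as stated.

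**2. Pooled correlation created by the arms.** Allocation is 1:1. Let dx be the arm difference in monocyte change and dy the arm difference in the outcome, both in within-arm SD units, and let ρ be the within-arm correlation. Then

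pooled r = (ρ + dx·dy/4) / sqrt[(1 + dx²/4)(1 + dy²/4)].

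The documents give no monocyte effect, so dx is an assumption. With ρ = 0 and dy = 0.56:
- dx = 0.5: 0.070 / sqrt(1.0625 × 1.0784) = 0.065
- dx = 0.8: 0.112 / sqrt(1.16 × 1.0784) = 0.10
- dx = 1.2: 0.168 / sqrt(1.36 × 1.0784) = 0.14

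**3. False-positive rate against a within-arm null.** Simulation with 52 per arm, normal errors, ρ = 0 and a two-sided 5% test. The other outcomes use the smallest change listed in Table 8 divided by its SD: central SBP 5/5.4 = 0.93, HOMA-IR 0.5/0.9 = 0.56, PWV 0.8/1.4 = 0.57.

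| Outcome (dy) | dx = 0 | dx = 0.5 | dx = 0.8 | dx = 1.2 | Arm-adjusted |
|---|---|---|---|---|---|
| PAV (0.56) | 5% | 10% | 17% | 29% | 5% |
| Central SBP (0.93) | 5% | 18% | 36% | 62% | 5% |
| HOMA-IR (0.56) | 5% | 10% | 17% | 29% | 5% |
| PWV (0.57) | 5% | 10% | 18% | 30% | 5% |

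Repeat runs differ by up to about one percentage point; for PAV at 0.8 SD they gave 17% to 18%. Over the wider range dx = 0.3 to 1.5, the PAV rate runs from 7% to 39%.

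**4. Dilution.** Take ρ = 0.3, dy = 0.56 and dx = −0.8. Pooled r = (0.3 − 0.112) / sqrt(1.16 × 1.0784) = 0.17. Power is about 40% pooled and 88% arm-adjusted. If ρ is −0.3 with the same shifts, pooled r = (−0.3 − 0.112)/1.118 = −0.37, so the association is reinforced. What matters is the sign of the between-arm product dx·dy relative to ρ. Movement in opposite directions is not enough by itself to mask an association.

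**The case against.** **Silence is not a choice.** A reader might infer that the plan has decided to ignore arm. It has not said so. It says only that the variables will be correlated, and a further SAP is promised. This objection stands, and the point is worded accordingly. But the text as written permits the pooled analysis, and the Aim 1 treatment term does not extend to it.

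**The size depends on an unseen input.** No monocyte effect is given, and the Study Rationale treats the effect of MR blockade on human monocyte inflammation as unknown. If the drug leaves either variable unchanged, the inflation disappears. For PAV the induced r is small: 0.14² is about 2% of variance. All of this stands. The harm is a raised error rate, and it appears when the drug works as the trial hopes. The Table 8 SDs are described as coming from reproducibility data. If the SD of change between patients is larger, the rates for central SBP and PWV would be lower.

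**A pooled r is a true marginal association.** It is false only against a within-arm null, which Aim 2b does not state. That is correct, but the marginal association adds little to the two arm comparisons already planned.

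**Two stronger readings are not supported.** One is that percent change in a subset percentage is an unstable measure. The wording may simply mean change in subset percentages, the general considerations already provide log and arcsine square-root transformations, and the documents give no baseline subset values from which to judge instability. The other is that adjusting for arm would settle the mechanism. A within-arm association between two post-randomisation variables remains open to patient-level confounding, and conditioning on arm also removes the between-arm variation that a true monocyte pathway would produce.

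**Conclusion.** The point holds as an unspecified arm adjustment that should be specified. On the trial's own premise that the drug moves both variables, an unadjusted correlation would mislead. For PAV at its design effect the false-positive rate against a within-arm null is about 10%, 17% and 29% at assumed monocyte shifts of 0.5, 0.8 and 1.2 SD, with expected r of about 0.07, 0.10 and 0.14. Central SBP is affected more (18%, 36% and 62%). HOMA-IR and PWV behave much like PAV. These figures rest on 104 completers, normal errors, zero within-arm association, and the full design or Table 8 effect on the outcome. With no monocyte shift the rate stays near 5%. A real association is diluted only when the between-arm shift opposes its sign. This is a secondary analysis, so the primary treatment comparison and the sample size are untouched.

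**What to change.** In Aim 2b and in the promised SAP, replace the correlation with one of two equivalent forms for each of PAV, HOMA-IR, central aortic SBP and PWV:
- a regression of the outcome at follow-up on its baseline value, the monocyte change and treatment arm; or
- a partial correlation of the two changes with arm partialled out.

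Report the estimate within each arm alongside. Use the transformations already named in Statistical Methods and Considerations (log for continuous measures, arcsine square root for percentages). Describe the result as a within-arm association, not as evidence of mediation.

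The cost is SAP wording and one degree of freedom for arm: in the correlation form, 104 − 3 = 101 residual degrees of freedom instead of 104 − 2 = 102. It needs no extra patients, visits or assays.
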